7. CONCOMITANT THERAPY

(1) Contraindicated drugs

Subjects will be prohibited from using the following drugs and all ophthalmic drugs including over-the-counter products (except artificial tears) during the period from study enrollment through the end of all examinations and observations.

If a subject is administered the following drugs, their dosage and administration must not be changed during the period from study enrollment through the end of all examinations and observations.

Antihistamines (oral or nasal), antidepressants (oral), retinoids (oral or topical), nonsteroidal anti-inflammatory drugs (topical) and niacin (oral).

(2) Contraindicated therapy

Surgical therapies affecting the ocular surface, such as intraocular surgery and ophthalmic laser surgery, are prohibited as concomitant therapies during the study period. Subjects considered requiring these surgical therapies should be withdrawn from the study and be treated appropriately.

8. DISCONTINUED SUBJECTS

(1) Discontinued Subjects

Subjects discontinued the study in the following cases:

- 1) Upon onset of adverse events which make study continuation difficult.
- 2) If the investigators judge it necessary to switch the therapy to another
- 3) The investigators judge to discontinue the study as deviation from inclusion and/or exclusion criteria after using the investigational products which has a problem in safety.
- 4) Upon cancellation of consent to the study by the subject.
- 5) Upon request of the subject to discontinue the study.
- 6) Hospital referral or move of the subject during the study, making it difficult to continue the study.
- 7) The use of ophthalmic drugs including over-the-counter products (except artificial tears) during the period from study enrollment through the end of all examinations and observations.

- 8) This was ineligible due to inclusion criteria and exclusion criteria.
- 9) If the investigators judge it necessary to discontinue the study.

Upon discontinuation of the study, if the investigators decided the examination or observation is necessary, the examination or observation should be carried out as far as possible under the subject's consent, and the date and reason of discontinuation are entered in the case report form.

In case where continuation of the study is difficult because of discontinued visit of the subject to the clinic, the subject is followed over telephone, by mail or other appropriate means and the reason for discontinued visit, survival/death of the subject, presence/absence of adverse events, etc., are entered in the case report form.

(2) Discontinuation of the entire study

If discontinuation of the entire study has become inevitable for reasons of reports on serious safety information from any participating study site or overseas, problems pertaining to the quality of the test articles, and so on, the Sponsor is required to immediately inform the investigator and the head of each study site of discontinuation of the study and its reason in writing.

9. ANALYSIS PLAN

(1) Evaluability

Evaluability of subjects and data will be determined before breaking masked key code and before locking the database lock.

1) Safety

The pre-treatment safety analysis set will include all subjects who consented to participate in the study. The pre-treatment safety analysis set will be the set that will be used to summarize occurrence of adverse experiences prior to exposure to the investigational products except for trial-fit lenses used at Visit 1. The treatment-emergent safety analysis set will include all eyes exposed to any investigational product evaluated in this study except for trial-fit lenses which is used at Visit 1.

2) Full Analysis Set(FAS)

The Full Analysis Set (FAS) includes all randomized subjects who are exposed to any investigational product except for trial-fit lenses which is used at Visit 1 and who complete at least 1 scheduled study visit.

3) Per Protocol Set(PPS)

The Per Protocol Analysis Set (PPS) includes all randomized subjects who are exposed to any investigational product except for trial-fit lenses which is used at Visit 1, who complete at least 1 scheduled study visit and who meet all inclusion criteria and do not meet any exclusion criteria.

The FAS and PPS will be used for primary efficacy analysis in the study. The FAS will be used for main results of primary efficacy analysis. [REDACTED]. The adverse experiences which occur in the period between informed consent and before exposure to the investigational

products will be analyzed by using data of subjects who consented to participate. The safety analysis after exposure to any investigational product will be performed with the Safety analysis set.

(2) Demographic factors and baseline characteristics

For demographic factors (gender, age [40-49 years, 50-59 years, 60-69 years, ≥ 70 years], type of habitual disposable multifocal SCL/SHCL, ocular medical history, concurrent diseases, and concomitant medications), the number and percentage of subjects will be calculated for all data sets (Safety Analysis Set, FAS, and PPS). For age, diopter of habitual disposable multifocal SCL/SHCL, average number of hours of wear per day and the average number of days of wear per week of habitual disposable multifocal SCL/SHCL, average number of hours of wear per day and total wearing days of investigational products, corneal curvature radius (keratometry), objective refraction (refractometry), subjective refraction (spherical equivalent), best corrected visual acuity with trial frame, and diopter of dispensed lenses, descriptive statistics (arithmetic mean, standard deviation, number of subjects, median, minimum, and maximum) will be calculated.

(3) Efficacy analysis

The primary objective of this study is to demonstrate non-inferiority in investigator-graded successful lens centration of DT1MF to AMMF after 14 ± 3 days of wearing. The primary efficacy analysis will be performed on the right or left eye that is randomly selected as a single study eye.

1) Primary analysis

The primary endpoint of this study is investigator-graded successful lens centration of “Optimal” after 14 ± 3 days of wearing.

[1] Statistical hypotheses

The null hypothesis (H_0) and alternative hypothesis (H_1) for the primary analysis are defined as follows:

$$H_0 : \pi_{(DT1)} - \pi_{(AM)} \leq -10\%$$

$$H_1 : \pi_{(DT1)} - \pi_{(AM)} > -10\%$$

[figure not shown]
[figure not shown]
Where $\pi_{(DT1)}$ and $\pi_{(AM)}$ denote the percentage of subjects rated as “Optimal” in the DT1MF and AMMF groups, respectively. The 10% is the non-inferiority margin.

[figure not shown]
[2] Method of analysis

The number and percentage of subjects rated as “Optimal” in investigator-graded lens centration assessment (after 14 ± 3 day of wearing) by each investigational product will be summarized, and a difference between two investigational products will be estimated by using confidence interval based on corresponding binomial test. Non-inferiority of DT1MF to AMMF will be demonstrated in case the lower one-sided 97.5% confidence limit of a difference between investigational lenses lies above -10%. If the crossover effect (DT1MF \rightarrow AMMF vs AMMF \rightarrow DT1MF) and/or the period effect (Visit 2 vs. Visit 3) are

found to be significant, DT1MF vs AMMF will be compared at each sequence and/or period separately.

Only if non-inferiority of DT1MF to AMMF is demonstrated, superiority of DT1MF over AMMF will be tested. Superiority will be demonstrated when the lower one-sided 97.5% confidence limit for investigational lens difference lies above 0%. P-value for McNemar test is also calculated. Non-inferiority and superiority hypothetical tests in above are based on the closed testing procedure; no adjustment of significance level for each test will be made.

(4) Handling of missing data

No imputation is planned for missing data.

(5) Multiplicity

Primary analysis will be performed a single variable, and superiority testing will be performed only when non-inferiority testing is demonstrated. [REDACTED]

[REDACTED] For defining the sequence of statistical testing in advance, the type I family-wise error (FWE) rate of [REDACTED] hypothesis tests which include primary efficacy analyses [REDACTED] is controlled at $\alpha = 2.5\%$ (one-sided). [REDACTED]

(6) Safety analysis

The number and percentage of adverse events and adverse experiences which occur in the period between informed consent and before exposure to the investigational products will be presented. For the following variables, observed values and their changes from baseline will be summarized. Continuous variables will be presented descriptive statistics (arithmetic mean, standard deviation, number of subjects, median, minimum, and maximum), whereas categorical variables will be presented the number and percentage.

- Slit-lamp examination
- Best corrected visual acuity with trial frame

(7) Medical economics analysis

No medical economics analysis is planned in the study.

(8) Interim analysis

No interim analysis is planned in the study.

(9) Rationale for the sample size

The sample size was estimated based on a subgroup analysis from a prior clinical study (CLE914-P001 study) in which 54 eyes were from habitual current AMMF wearers. In terms of investigator-graded lens centration after 14±3 days of wearing, a difference was showed that DT1MF had 13.0% better percentage of “Optimal” than AMMF (See the table below).

Table Lens centration assessment by investigator (14±3 days of wearing) (CLE914-P001, Unit: Eye)

		AMMF			Difference between investigational device (DT1MF – AMMF)
		Optimal	Other than Optimal	Total	
DT1MF	Optimal	45	7	52	7
		83.3%	13.0%	96.3%	13.0%
	Other than Centered/ Optimal	0	2	2	\
		0%	3.7%	3.7%	
	Total	45	9	54	
		83.3%	16.7%	100%	

With 120 subjects (one study eye per one subject), the probability that a lower limit of 97.5% one-sided confidence interval of lens difference lies above -10% is more than 99% and the probability of lens difference lying above 0% is 92%, assuming the percentage of "Optimal" in population is the same as in the table above.

[REDACTED]

As the 120 patients are required for the effectiveness assessment in this study, the 134 patients will be enrolled in order to assume around 10 % discontinuation.

10. ADVERSE EVENTS and DEVICE DEFICIENCIES, etc.

Adverse events will be collected from the time of informed consent even if the investigational product isn't allocated.

(1) General Information

Refer to the Glossary of Terms below for categories of AEs and SAEs.

Adverse Event (AE):

Any untoward medical occurrence, unintended disease or injury, or untoward clinical signs (including abnormal laboratory findings) in subjects after signed informed consent, users or other persons, whether or not related to the investigational medical device (test article). *For subjects, this definition includes events related to the test article or the procedures involved. For users or other persons, this definition is restricted to events related to the test article.*

Serious Adverse Event:

Adverse event that led to any of the following, or that needed treatment not to lead to the following results:

- Death.
- A serious deterioration in the health of the subject that either resulted in:
 - a) a life-threatening illness or injury.

Note: Life-threatening means that the individual was at immediate risk of death from the event as it occurred, ie, it does not include an event which hypothetically might have caused death had it occurred in a more severe form.

- b) any potentially sight-threatening event or permanent impairment to a body structure or a body function.
- c) in-patient hospitalization or prolonged hospitalization.

Note: Planned hospitalization for a pre-existing condition, without serious deterioration in health, is not considered a serious adverse event. In general, hospitalization signifies that the individual remained at the hospital or emergency ward for observation and/or treatment (usually involving an overnight stay) that would not have been appropriate in the physician's office or an out-patient setting. Complications that occur during hospitalization are adverse events. If a complication prolongs hospitalization or fulfills any other serious criteria, the event is serious. When in doubt as to whether "hospitalization" occurred, the event should be considered serious.

- d) a congenital anomaly/birth defect,

e) a medically important event or reaction.

Non-serious Adverse Event

Adverse event that does not meet the criteria for a serious adverse event.

Adverse Device Effect (ADE)

Adverse event related to the use of an investigational medical device (test article).

Note: This definition includes adverse events resulting from insufficient or inadequate instructions for use, deployment, implantation, installation, or operation; any malfunction; and use error or intentional misuse of the test article.

Serious Adverse Device Effect (SADE)

Adverse device effect that has resulted in any of the consequences characteristic of a serious adverse event.

Device Deficiency

Inadequacy of a medical device with respect to its identity, quality, durability, reliability, safety, or performance.

Safety Information:

Information about quality, efficacy and safety for medical device and information which is needed for appropriate use, including:

- Use error
- Abnormal Use
- Product tampering
- Product counterfeiting
- Product theft

(2) Procedure for Reporting of serious adverse events (SAE)

The investigator will report the serious adverse event or the risk of causing serious adverse event to Alcon within 24 hours after confirming the event.

After obtainment of detailed information on the serious adverse event, the investigator will prepare a report and immediately submit it to Alcon and the head of the medical institutions.

Contact for emergent communication

Alcon Japan Ltd. Clinical Development, CDMA & Regulatory Affairs, Japan.

TEL [REDACTED] (At night and on holidays: [REDACTED])

FAX [REDACTED]

When the SAE is correspond to “Death or a life-threatening ADE” or “Serious and unexpected ADE other than Death or a life-threatening event”, the sponsor will immediately notify them to heads of all medical institutions and all investigators by document.

(3) Report of adverse events and evaluation of the causal relationship

All adverse events (related and unrelated to the medical device) will be documented on the Adverse Event Case Report Form (CRF).

AEs will be sorted into the investigational product by the following periods (Onset time of AE), because this study is cross-over design.

Periods: Onset time of AE	investigational product
Informed consent to Visit 1: baseline	N/A
Visit 1: Dispensing Lens 1 to Visit 2: Follow Up Lens1	Lens 1
Visit 2: Dispensing Lens 2 to Visit 3: Follow Up Lens2	Lens 2

(4) Intensity Assessment of Adverse Events

For every AE, the investigator must assess the intensity (severity). Events should be classified as mild, moderate, or severe. These classifications should be based on the following definitions:

Intensity:

Mild An AE is mild if the subject is aware of but can easily tolerate the sign or symptom.

Moderate An AE is moderate if the sign or symptom results in discomfort significant enough to cause interference with the subject's usual activities.

Severe An AE is severe if the sign or symptom is incapacitating and results in the subject's inability to work or engage in their usual activities.

(5) Follow-up of Subjects / Subjects with Adverse Events

In the event of acknowledging any adverse events, the investigators should immediately take appropriate actions irrespective of the presence or absence of causal relationship with the test article. And the investigators will make a follow-up of the adverse event if it is possible. When the subject needs medical treatment, the investigators should inform the subject of the matter.

For subjects who are experiencing ongoing unresolved adverse events at the time of their study completion or early discontinuation from the study, it is recommended that the investigator schedule an appropriate follow-up visit in order to determine the outcome of the event.

(6) Pregnancy of subjects

Women who is planning to become pregnant during this study period or women who are pregnant at the time of study entry are excluded from participation

(7) Provision of safety information

Investigators provide safety information which is needed to make a detailed report on demand from the sponsor.

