- [1] Observe the ocular anterior segment with Lens 1 by slit-lamp microscopy.
- [2] Assess lens centration [REDACTED] (10-15 min post insertion) for Lens 1 by slit-lamp microscopy

according to Section 6-(5) "Evaluation Method", 1) "Lens centration" [REDACTED]
[REDACTED]

- [3] If any specification adjustment is required, repeat the procedures from [1] to [3] above.
- [4] [REDACTED]
- [5] Confirm information on the dispensed Lens 1 (type, diopter and lot number).
- [6] Confirm the presence or absence of adverse events and device deficiencies. If any adverse event and/or device deficiencies is present, record data on the event in the Adverse Event CRF according to Section 10 "Adverse Events and Device Deficiencies, etc." of the protocol.
- [7] Schedule the next visit (Visit 2) date. Dispense necessary number of Lens 1 to the subject. Instruct the subject to contact the investigator, etc. if he/she feels any abnormality. If lens has any device deficiencies, let the subject bring it on Visit 2.

3) Visit 2: Follow up CL1

- [1] Confirm the time of Lens 1 insertion and the start and end times of examinations on the visit day (and document these times in the medical record).
- [2] Confirm the change of concomitant medications, etc.
- [3] Confirm whether Lens 1 is used appropriately during the period between the last and present visits (total days of Lens 1 wearing, average of wearing time per day. If subjects visit the clinic without wearing Lens 1, confirm the reason).

[REDACTED]
[REDACTED]
[REDACTED]

- [7] Assess lens centration [REDACTED] for Lens 1 by slit-lamp microscopy according to Section 6-(5) "Evaluation Method", 1) "Lens centration" [REDACTED]
[REDACTED]
- [8] Remove Lens 1, and assess fluorescein corneal and conjunctival staining by slit-lamp microscopy according to Section 6-(5) "Evaluation Method" 5) "Corneal staining" and Section 6-(5) "Evaluation Method", 6) "Conjunctival staining"
- [9] Measure best corrected visual acuity with trial frame.
- [10] Confirm the presence or absence of adverse events and device deficiencies with reference to subjective questionnaire answers. If any adverse event and/or device deficiencies is present, record data on the event in the Adverse Event CRF according to Section 10 "Adverse Events and Device Deficiencies, etc." of the protocol.

4) Visit 2 Disp. CL 2

- [1] Observe the ocular anterior segment with Lens 2 by slit-lamp microscopy.

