- [2] Assess lens centration [REDACTED] (10-15 min post insertion) for Lens 2 by slit-lamp microscopy according to Section 6-(5) "Evaluation Method", 1) "Lens centration" [REDACTED]
[REDACTED]
- [3] If any replacement in specification is required, repeat the procedures from 1 to 3 above.
[REDACTED]
- [5] Confirm information on the dispensed Lens 2 (type, diopter and lot number).
- [6] Confirm the presence or absence of adverse events and device deficiencies. If any adverse event and/or device deficiencies is present, record data on the event in the Adverse Event CRF according to Section 10 "Adverse Events and Device Deficiencies, etc." of the protocol.
- [7] Check the date of the next visit (Visit 3), and tell the subject to bring habitual multifocal SCL/SHCL or glasses when follow up visit. Dispense necessary number of Lens 2 to the subject. Instruct the subject to contact the investigator, etc. if he/she feels any abnormality. If lens has any device deficiencies, let the subject bring it on Visit 2.

5) Visit3: Follow up CL2

- [1] Confirming the time of Lens 2 insertion and the start and end times of examinations on the visit day (and document these times in the medical record).
- [2] Confirm the change of concomitant medications, etc.
- [3] Confirm whether Lens 2 is used appropriately during the period between the last and present visits (total days of Lens 2 wearing, average of wearing time per day). If subjects visit the clinic without wearing Lens 2, confirm the reason.

[REDACTED]
[REDACTED]
[REDACTED]
[REDACTED]
[REDACTED]
[REDACTED]

- [7] Assess lens centration [REDACTED] for Lens 2 by slit-lamp microscopy according to Section 6-(5) "Evaluation Method", 1) "Lens centration" [REDACTED]
[REDACTED]
- [8] Remove Lens 2, and assess fluorescein corneal and conjunctival staining by slit-lamp microscopy according to Section 6-(5) "Evaluation Method", (5) "Corneal staining" and Section6-(5) "Evaluation Method", (6) "Conjunctival staining"
- [9] Measure best corrected visual acuity with trial frame.
- [10] Confirm the presence or absence of adverse events and device deficiencies with reference to subjective questionnaire answers. If any adverse event and/or device deficiencies is present, record data on the event in the Adverse Event CRF according to Section 10 "Adverse Events and Device Deficiencies, etc." of the protocol.

6) **Unscheduled Visit (To conduct examinations as needed)**

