- [1] At unscheduled visit resulting from adverse events, etc., confirm the reason for visit and procedures taken during the visit.
- [2] Identify the type of the study lens used by the subject.
- [3] Perform examinations, assessments, or confirmations considered necessary by the investigator among those listed below:
 - Best corrected visual acuity with trial frame
 - [REDACTED]
 - Lens centration [REDACTED]
 - Slit-lamp microscopy examination (including sodium fluorescein corneal, etc.).
 - Information on the investigational products (diopter and lot number), if changed
 - [REDACTED]
- [4] Dispense the required number of the study lens to the subject, as needed.
- [5] Confirm the presence or absence of adverse events. If any adverse event is present, confirm the items in the Adverse Event CRF according to Section 10 “Adverse Events and Device Deficiencies, etc.” of the protocol.

(5) **Evaluation Method**

1) **Lens centration**

Assess lens centration for each eye by slit-lamp microscopy according to the criteria shown below.

For assessment results other than “Optimal”, check the direction of lens decentration (upward, downward, nasal, or temporal).

[figure not shown]
	Criteria
0	Centered/ Optimal
1	Slight decentration
2	Mild decentration (without limbal touch)
3	Moderate decentration (with limbal touch but without corneal exposure)
4	Severe decentration (with corneal exposure)

[figure not shown]
2) [REDACTED]

[figure not shown]
[REDACTED]

[REDACTED]

[REDACTED]

[figure not shown]
4) Fluorescein corneal and conjunctival staining

Corneal and conjunctival staining with fluorescein of both eyes will be rated by the investigator using a 5 point scale (0= Normal, 1= Trace, 2=Mild, 3=Moderate, 4=Severe).

Corneal staining with fluorescein (EFRON GRADING)

Conjunctival staining with fluorescein (EFRON GRADING)

(6) Anticipated study period

From NOVEMBER 2017 to OCTOBER 2018

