1.2 Study Description

This is a prospective, multi-center, single masked (subject), randomized¹ and crossover study. Subjects will be randomly assigned to one of the two orders of the investigational product wearing (DT1MF to AMMF or AMMF to DT1MF) at a ratio of 1:1 using the permuted block randomization. Subjects will wear each study article (DT1MF and AMMF) in both eyes for at least 11 days each. The randomization manager will also create the randomization code for the study eye (right or left) and maintain the key code in a masked state² until the time of code breaking.

The subject who wears habitual presbyopic soft/silicone hydrogel contact lens (multifocal lenses only) with a near spectacle ADD of +0.50D to +2.50D (inclusive) will be enrolled. The subjects will wear each of the investigational products for 14±3 days. During the observation period, the subjects remove and discard the lenses every night and use a new pair of lenses every morning. As 120 patients are required for the effectiveness assessment in this study, 134 patients will be enrolled assuming around ten percent discontinuation. One eligible eye for effectiveness analysis will be randomly selected as a study eye according to the permuted block randomization. Scheduled Visits are listed in Table 1-1, as follows.

Table 1-1 Schedule of Study Visit

Days from Dispensing		Study Visit
Visit 1	Pre-Dispensing	Visit 1: Baseline Visit
	Dispensing CL1	Visit 1: Dispensing CL1
Visit 2	14 ± 3 Days after dispensing CL1	Visit 2: Follow up CL1
	Dispensing CL2	Visit 2: Dispensing CL2
Visit 3	14 ± 3 Days after dispensing CL2	Visit 3: Follow up CL2

¹ The sequence of study lens use (DT1MF to AMMF or AMMF to DT1MF) is randomized in this study. The subjects wear the same lens in both eyes.

² The randomization code for sequence of study lens use will be masked only to the subjects. The randomization code for the target eye must be masked for the site, the subjects and sponsor.

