2.1 Efficacy Analysis Sets

Full Analysis Set (FAS):

The Full Analysis Set (FAS) includes all randomized subjects who are exposed to any investigational product except for trial-fit lenses which is used at Visit 1 and who complete at least 1 scheduled study visit.

Per Protocol Analysis Set (PPS):

The Per Protocol Analysis Set (PPS) includes all randomized subjects who are exposed to any investigational product except for trial-fit lenses which is used at Visit 1, who complete at least 1 scheduled study visit and who do not meet any of the critical deviation or evaluability criteria identified in the Deviations and Evaluability Plan (DEP).

The FAS and the PPS will be used for primary effectiveness analysis in this study. The FAS will be used for main interpretation of primary effectiveness results. [REDACTED]

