4.3 Statistical Methods for Efficacy Analyses

4.3.1 Primary Effectiveness Analysis

The primary effectiveness objective of this study is to demonstrate non-inferiority of DT1MF to AMMF for investigator-graded successful lens centration after 14 ± 3 days of wearing, more specifically, non-inferiority of DT1MF to AMMF will be demonstrated in case the lower one-sided 97.5% confidence limit of a treatment proportion difference lies above -10%.

If and only if non-inferiority is demonstrated, superiority of DT1MF over AMMF in Investigator-graded lens centration of “Optimal” will be tested. The superiority of DT1MF to AMMF will be demonstrated when a 97.5% one-sided lower confidence limit of lens difference lies above 0%.

If the Sequence (Crossover) Effect (DT1MF→AMMF vs AMMF→DT1MF) and/or the Period Effect (Visit 2 vs. Visit 3) are found to be significant, DT1MF vs AMMF will be compared at each period and/or sequence separately.

Period Effect and Sequence Effect (Crossover Effect) will be investigated with the three-way table classifying four types of response by each sequence group (Table 4-3).

Table 4-2 Analysis of Period Effect and Sequence Effect for Crossover Study

Sequence Group	Period Effect		Sub Total	Sequence Effect		Sub Total	Total
	DT1MF Optimal & AMMF Non- Optimal	DT1MF Non- Optimal & AMMF Optimal		DT1MF Optimal & AMMF Optimal	DT1MF Non- Optimal & AMMF Non-Optimal		
DT1MF→AMMF	n111	n112	n11.	n211	n212	n21.	n.1.
AMMF→DT1MF	n121	n122	n12.	n221	n222	n22.	n.2.
p-value*	0.XXXX		n1..	0.XXXX		n2..	n

[figure not shown]
*Fisher's Exact Test

If there were Period Effect and both sequence groups had propensity to have more “Optimal” in the second period, the proportion of n112 and n121 should be larger. Or, if there were Period Effect and both sequence groups had propensity to have less “Optimal” in the second period, the proportion of n111 and n122 should be larger (Mainland-Gart) [2], [3], [4].

On the other hand, if there were Sequence Effect that DT1MF had propensity to have more “Optimal” in the first period and AMMF had propensity to have more “Optimal” in the second period, the proportion of n211 and n222 should be larger. Or, if there were Sequence Effect and DT1MF had propensity to have more “Optimal” in the second period and AMMF

had propensity to have more “Optimal” in the first period, the proportion of n212 and n221 should be larger (Hills-Armitage) ^{[2], [5]}.

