Fisher’s exact test will be performed to add statistical insight in addition to descriptive statistics, although the statistical power might not be necessarily maintained due to insufficient sample size.

[figure not shown]

Table 4-4 summarizes the key effectiveness analyses.

Table 4-4 Summary of Analysis Strategy for Primary [REDACTED] Efficacy Endpoints

Endpoint	Main vs. Sensitivity Approach ^a	Statistical Method ^b	Analysis Set	Missing Data Approach
Primary				
Investigator-graded successful lens centration after 14±3 days of wearing	M	Unmodified Wald method	FAS (Study Eye)	Observed data only
Investigator-graded successful lens centration after 14±3 days of wearing	S	Unmodified Wald method	PPS (Study Eye)	Observed data only
Investigator-graded successful lens centration after 14±3 days of wearing	S	Unmodified Wald method	FAS (Non-Study Eye)	Observed data only

^aM=Main analysis approach; S=Sensitivity analysis approach

^bFurther details on statistical models are:

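### Does the primary analysis need a sensitivity analysis that varies the missing-data assumption?

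*Protocol*

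**What the plan says.** Protocol section 9(4) has one rule for missing data: "No imputation is planned for missing data". SAP Table 4-4 agrees with it. The main row (full analysis set, study eye) and the two visible sensitivity rows (per-protocol set, study eye; full analysis set, non-study eye) all use the unmodified Wald method with "Observed data only".

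SAP section 4.2 estimates the difference as (f − g)/n, where the four cells e, f, g and h of the paired table add up to n. Only a subject graded on both lenses has a cell. Entry to the full analysis set is wider: SAP section 2.1 asks for randomised subjects who were exposed to a study lens "and who complete at least 1 scheduled study visit". Protocol section 9(9) and SAP section 8 require 120 subjects and enrol 134, to allow for around 10% discontinuation.

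**The concern.** The full analysis set can hold subjects with only one 14-day grade, and these drop out of the main estimate. Neither visible sensitivity row brings them back.

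- **Per-protocol row.** This set is narrower, so it recovers nobody.
- **Non-study-eye row.** It cannot help with a missed visit. SAP section 1.2 says "The subjects wear the same lens in both eyes", and Protocol section 6(5) says "Assess lens centration for each eye by slit-lamp microscopy according to the criteria shown below". Both eyes are graded at the same visit, so both grades go missing together.
- **By-period comparison.** SAP section 4.3.1 says "DT1MF vs AMMF will be compared at each period and/or sequence separately", but only if a period or sequence effect is significant.

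Protocol section 8(1) lists reasons for discontinuation that could relate to the lens, such as adverse events or the investigator's judgement that a switch is needed. The investigators who grade centration also know the lens sequence. If dropouts did worse on DT1MF than completers, the main result would be too favourable, and none of the visible rows would show it. The non-inferiority claim, and the superiority claim that may follow, would be at stake.

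**Working it through.** **Size of the loss.** 120/0.9 = 133.3, which rounds up to the plan's 134. The planning allowance is therefore 134 − 120 = 14 subjects without a complete pair.

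**Formula (SAP section 4.2).** Lower limit = (f − g)/n − 1.96 × √(f + g − (f − g)²/n)/n. Here f counts pairs Optimal on DT1MF only and g counts pairs Optimal on AMMF only. To test the missing pairs, set n = 134, add k of the 14 to g and treat the other 14 − k as concordant.

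**At the planned effect.** SAP Table 8-1 has 7 of 54 discordant pairs favouring DT1MF and 0 against. For 120 pairs, 120 × 7/54 = 15.6, so take f = 16 and g = 0.

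- Complete pairs: 16/120 − 1.96 × √(16 − 256/120)/120 = 13.33% − 6.08% = +7.25%.
- All 14 adverse: 2/134 − 1.96 × √(30 − 4/134)/134 = 1.49% − 8.01% = −6.51%. Non-inferiority holds.
- Superiority: +0.72% at k = 6 and −0.21% at k = 7, so it is lost at 7.

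**Can 7 adverse pairs arise?** A subject lost in period 2 keeps the period 1 grade. In the AMMF-first sequence the pair can turn adverse only if the AMMF grade was Optimal (45/54). In the DT1MF-first sequence it can do so only if the DT1MF grade was not Optimal (2/54). With 7 losses per sequence, the expected number of pairs able to turn adverse is 7 × 45/54 + 7 × 2/54 = 6.09, below 7. To reach 7 on average takes one of two patterns:

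- At least 9 of the 14 losses fall in the AMMF-first sequence: 9 × 45/54 + 5 × 2/54 = 7.69 (with 8 it is 6.89).
- At least 2 losses occur before Visit 2 and the rest are balanced: 2 + 6 × 47/54 = 7.22 (with 1 it is 6.66).

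Even then, nearly every pair that could turn adverse would have to do so.

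**If the observed difference is zero.** This is an assumed case; the documents give no such result. The last column is the chance P(Bin(14, g/120) ≥ k) when dropouts resemble completers.

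| f, g | Complete-pairs limit | Limit at k − 1 | Limit at k | k that loses non-inferiority | Chance |
|---|---|---|---|---|---|
| 4, 4 | −4.62% | −9.90% | −10.82% | 7 | below 0.01% |
| 6, 6 | −5.66% | −9.73% | −10.64% | 6 | below 0.01% |
| 8, 8 | −6.53% | −9.51% | −10.40% | 5 | 0.16% |
| 10, 10 | −7.30% | −9.24% | −10.13% | 4 | 2.4% |

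With equal success rates and 7 period 2 losses per sequence, about 7 pairs could turn adverse. So 7/7, 6/7, 5/7 or 4/7 of them (100%, 86%, 71%, 57%) would have to.

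The chances are also on the high side, because no missing pair is allowed to favour DT1MF. If favourable and adverse pairs are both drawn at the observed rates, the last two fall to 0.09% and 1.1%.

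**The case for a change.** The strongest case for the concern lies with superiority at results between zero and the planned effect. With f = 12 and g = 4 (+6.7 points) the complete-pairs limit is +0.24%, and one adverse pair removes superiority. With 10 and 2 it is +1.14%, lost at two; with 11 and 1 it is +2.88%, lost at three. Balanced period 2 losses could supply that many. Dropout may also be informative, and the benchmark of dropouts resembling completers does not exclude that. A tipping-point row would be cheap and would use data already collected.

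The arithmetic stands, and so does the description of the visible rows. Three things limit what follows.

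- Those superiority cases are assumed results that already lie close to zero. Any such result is sensitive to a few subjects; that is not a defect of the missing-data rule. The study objective and the visible success criterion in the SAP are non-inferiority.
- The documents give no evidence of informative dropout, and the direction of any bias is unknown.
- The basic bound needs only the four paired counts and the number of incomplete pairs, so a reader can compute it if these are reported. Only the version that holds observed single grades fixed needs subject-level data. The dispensing grades ("10-15 min post insertion) for Lens 1 by slit-lamp microscopy" and "10-15 min post insertion) for Lens 2 by slit-lamp microscopy") would add little: the lens specification may be adjusted and the assessment repeated, so they lean towards good centration.

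The visible text is also incomplete. Table 4-3 is not shown, parts around the analysis sets are redacted, and the Deviations and Evaluability Plan is not available. Protocol section 9(3) further plans counts and percentages of Optimal grades by product. Its text does not fix their denominator, so they could include subjects with one grade.

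**Conclusion.** The concern does not hold. The protocol and SAP state the same explicit rule, and applying it gives a sound primary result. At the planned effect, non-inferiority survives all 14 allowed losses being counted against DT1MF (limit −6.51% against a −10% margin). Superiority needs 7 adverse pairs, against about 6.1 possible with balanced period 2 losses. Only an assumed result near zero exposes non-inferiority, and there the chance of tipping is at most 2.4% in the cases examined.

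This rests on about 14 incomplete pairs, the planning rates of SAP Table 8-1, and dropouts resembling completers where a probability is given. Much heavier or clearly lens-related dropout would call for a closer look at the data. An extra tipping-point table is a matter of preference: it would change neither the main analysis nor the conclusion the trial can draw.
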